3. STUDY DESIGN

The EMMED-HF trial will be a single blinded (to patient), randomized, parallel group, active controlled, single center experimental design. 52 subjects with HFpEF and DM2 will comorbidities will be recruited to participate (N = 26 ertugliflozin group, N = 26 placebo group) with a 12 week study intervention period.

Enrollment/Randomization procedure

Subjects will be screened by qualified practitioners for eligibility to participate in the EMMED-HF clinical study. Once the subject has been determined to be eligible, an enrollment visit will be scheduled. Those subjects that meet the inclusion criteria and do not possess any exclusion criteria will be deemed eligible for enrollment by key study personnel and then undergo randomization to treatment arm. Randomization into treatment group will occur at baseline at a 1:1 ratio.

Primary endpoint

The primary endpoint is to assess the degree of change in peak exercise oxygen uptake (peak VO2, ml/kg/min) as measured by metabolic gas exchange during a MRIcardiopulmonary exercise test (CPET-ExMR) protocol.

Secondary endpoints

Change in LV mass index (gm/m2) measured by MRI imaging will be a pre-specified secondary endpoint. An additional pre-specified secondary endpoint will be fasting serum β -hydroxybutyrate (ketone body).

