Visit #3: Follow up Testing: At the end of the study intervention period, but prior to the completion of the study medication package (during week #12), the subject will undergo a repeat of the same battery of clinical testing as during Visit #2. Each test will be conducted with an identical protocol to allow for intra-subject assessment of change. Testing during Visit #3 will include: Transthoracic Echocardiography

Cardiopulmonary Exercise Cardiac Magnetic Resonance Imaging (CPET-ExMR) Dual-energy absorptiometry (DEXA) Serum Chemistries & Metabolomics

Symptom Surveys

Study Completion: At the end of the 12 week intervention period, after the subject has completed screening (visit #1), baseline (visit #2), and end of study (visit #3) testing, a SUBJECT COMPLETION CRF must be completed. During the course of the study, it is possible that subjects will be withdrawn from the study. Factors leading to Subject early termination may include, but are not limited to the following.

Subject Withdrawal - A Subject may voluntarily withdraw from the study at any time without affecting their future medical treatment or benefits. In addition, the Investigator may withdraw a Subject from the study if the enrolled Subject does not meet the inclusion/exclusion criteria,

refuses further testing or follow-up evaluations, or for any other reason as determined by the Investigator. A SUBJECT TERMINATION CRF must be completed.

Subject Lost to Follow-Up – If the Investigator has attempted to contact a Subject at least three times and receives no response, the Subject is considered lost to follow-up. The research staff should document at minimum three attempts to contact the Subject, including a certified letter, prior to terminating a Subject from the trial. A SUBJECT COMPLETION CRF must be completed. Subject Death – The Investigator will notify the UH IRB, the local DSMB, the FDA and the Sponsor within 7 days of knowledge of a subject's death. An ADVERSE EVENT and SUBJECT COMPLETION CRF must be completed, as well as a report from the Investigator explaining the nature of the Subject's death.

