6. INTERVENTION DISCONTINUATION

Study procedures and interventions will be discontinued immediately if the any of the following occur:

- Volunteer decides that he/she would no longer like to continue with the study
- Side effects of the study drug prevent further safe use
- Study personnel identify a concern with the condition of the subject

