7. STATISTICAL CONSIDERATIONS

7.1 Data analysis

Data analysis and statistical evaluation will be the responsibility of the primary investigator ([name]) using statistician resources at UH Cleveland Medical Center Harrington Heart and Vascular Institute (CWRU CTSC Biostatistics Core). Data will be collected in a secure REDCap database that is housed at our institution in accordance with local IRB regulations. Blinding will be maintained by the study team. Medications given to subjects will be labeled "study medication" to maintain subject blinding to treatment status and will be dispensed by the UHCMC Research Pharmacy for each subject after successful enrollment. For the purpose of the final analysis, the official clinical database will not be unblinded until medical/scientific review has been completed, protocol violators have been identified (if appropriate), and data has been declared complete.

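### Open-ended investigator withdrawal can remove randomised subjects from the primary comparison, and no as-randomised analysis rule protects against it

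*Combined protocol and SAP*

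**What the plan says.** **Withdrawal.** Section 4.4 (Study Completion) introduces its list of reasons with "Factors leading to Subject early termination may include, but are not limited to the following". It then provides that "the Investigator may withdraw a Subject from the study if the enrolled Subject does not meet the inclusion/exclusion criteria", and extends this to a subject who "refuses further testing or follow-up evaluations, or for any other reason as determined by the Investigator". The only stated consequence is administrative: "A SUBJECT TERMINATION CRF must be completed". Section 6 adds a separate route that stops both procedures and intervention; one of its triggers is "Study personnel identify a concern with the condition of the subject".

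**Blinding.** Section 3 says: "The EMMED-HF trial will be a single blinded (to patient), randomized, parallel group". Section 1 also describes the blind as applying to the subject. Section 4.4 (Group assignment protocol) names the statistician as the unblinded person, uses A/B treatment codes, and has the statistician deal directly with the pharmacy. Section 7.1 has the study team maintaining the blind, and has protocol violators identified before the database is unblinded.

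**Timing of randomisation.** Section 3 and the group assignment text put it at baseline, after eligibility is accepted. The heading for Visit #1 in section 4.4 names randomisation together with screening, at the visit where screening laboratory tests are listed.

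**Analysis.** Section 7.2 gives a t test or a Wilcoxon test for continuous variables. In the text available for review, which lacks most of section 9, there is no analysis population, no handling of missing outcomes and no allowance for dropout.

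**The concern.** Randomisation protects the comparison only if subjects stay in it for reasons unrelated to arm and outcome. Here an enrolled subject, possibly already randomised, can be taken out on open discretion or because an eligibility failure is noticed late. The primary endpoint needs a Visit #3 measurement, so early withdrawal also means losing the outcome.

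Late ineligibility is a realistic route because the entry rules leave room for interpretation. Section 4.2 excludes haemoglobin below 11.0 (women) or 12.0 (men), while the physical screening list in section 4.4 asks for values above 11.5 or 12.5. A woman at 11.2 passes one rule and fails the other. The same list requires that the volunteer appear to be in good health.

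With 26 subjects per arm, each subject carries about 4% of an arm mean (1/26), so a few selective losses matter.

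**Working it through.** **1. Does the rule reach randomised subjects?** Section 3: approval for enrolment, then randomisation. Section 4.4: the withdrawal rule applies to an enrolled subject. Nothing limits it to the time before randomisation, so it does.

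**2. Does withdrawal remove the primary outcome?** The schedule in section 4.3 shows the metabolic cart at Visit #2 and Visit #3 only, with phone calls at weeks 4 and 8 between them. Withdrawal before Visit #3 leaves no post-baseline peak VO2. Since section 7.2 specifies only a two-sample test, that subject contributes nothing to it.

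**3. The plan's own sample size.** The section 7.2 inputs are k = 2, alpha 0.05, beta 0.2 and f = 0.4. For two equal groups d = 2f = 0.8.
- Normal approximation: n per arm = 2(1.960 + 0.842)²/0.8² = 24.5, so 25.
- Exact t test: 25.5, so 26 per arm and 52 in total, as planned.

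(With SD 2.0, d = 0.8 corresponds to 1.6 ml/kg/min, not the 2.0 in the text. That is a separate matter.)

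Power at d = 0.8 is 80.7% with 26/26, 79.1% with 26/24, 77.4% with 24/24 and 73.6% with 22/22. There is no slack for withdrawals.

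**4. Size of the bias if removal is selective.** From the plan: 26 per arm and SD 2.0, taken as the SD of change. Assumed, and not in the documents: no true effect; k subjects removed from one arm only; those removed are the ones who look worst to the investigator; and the investigator's impression correlates ρ with the true change.

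Expected shift = ρ × SD × |sum of the k lowest expected standard normal order statistics of 26| / (26 − k).

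For k = 2 the two order statistics are −1.982 and −1.544:
- ρ = 0.3: 0.3 × 2.0 × 3.526/24 = 0.09 ml/kg/min
- ρ = 0.5: 0.5 × 2.0 × 3.526/24 = 0.15 ml/kg/min
- ρ = 1.0: 1.0 × 2.0 × 3.526/24 = 0.29 ml/kg/min

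Type I error comes from simulating null trials with a two-sided t test on those remaining. Ranges show the spread between separate runs of at least 100,000 trials.

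| k removed | Quantity | ρ = 0.3 | ρ = 0.5 | ρ = 1.0 (upper bound) |
|---|---|---|---|---|
| 1 | Shift, ml/kg/min | 0.05 | 0.08 | 0.16 |
| 1 | Type I error | 5.0–5.1% | 5.4% | 6.6–6.7% |
| 2 | Shift, ml/kg/min | 0.09 | 0.15 | 0.29 |
| 2 | Type I error | 5.3–5.4% | 5.9–6.1% | 9.3–9.5% |
| 4 | Shift, ml/kg/min | 0.16 | 0.27 | 0.54 |
| 4 | Type I error | 6.0–6.2% | 7.8% | 18.0% |

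Because the selection runs in one direction, the two-sided rate understates the effect on results favouring drug. For k = 2, that rate rises from 2.5% to about 3.6% (ρ = 0.3), 4.6% (ρ = 0.5) or 8.4–8.5% (ρ = 1.0).

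**The case against.** A reader might infer from the single-blind label that the investigator knows the arm and that the protocol therefore permits arm-based removal. The documents do not support that. Only the statistician is named as unblinded, treatments are coded, both arms carry the same label, and violators are identified before the database is unblinded. Equally, no text says that the investigator is blinded: the sentence that follows the section 7.1 statement on blinding concerns the subject's blind, and the pre-unblinding review does not govern withdrawals during the 12 weeks. What stands is that the investigator's blinding is unclear.

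A reader might also take the 9.5% as the expected error rate. It is not. Nobody can rank subjects on change in peak VO2 before Visit #3, and the scheduled contacts in between are two phone calls. The lower correlations are the more plausible case, and they too are assumptions.

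Third, section 4.4 never says that withdrawn subjects leave the analysis. That is correct; the loss follows from the single post-baseline measurement and the absence of any rule for missing outcomes.

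Finally, requiring follow-up to Visit #3 without exception would conflict with section 6, since that visit includes exercise MRI with contrast. This stands and limits the remedy.

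**Conclusion.** The concern holds in a limited form. The withdrawal rule, the single post-baseline measurement and the silence of section 7 together allow randomised subjects to be lost selectively from the primary comparison. The text makes this possible; it does not show that it will happen. If the investigator is in fact blinded, arm-based removal becomes unlikely, but exclusions after randomisation would still lack an analysis rule.

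For two one-sided removals under the assumed correlations of 0.3 to 0.5, the shift is 0.09/2.0 = 4.5% to 0.15/2.0 = 7.5% of the 2.0 ml/kg/min difference the plan states, with a small rise in type I error. The result scales with the number removed and the accuracy of selection, neither of which the documents give. This is an inexpensive improvement that should be made, not a fatal flaw.

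**What to change.** In section 7:
- Define the primary analysis as all randomised subjects in their assigned arm, with a pre-specified method for missing Visit #3 outcomes.
- Use protocol violators, identified before unblinding, only to define a supportive per-protocol analysis.

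In section 4.4:
- Separate stopping study drug from leaving follow-up.
- State that ineligibility found after randomisation, or open-ended discretion, is not by itself a ground for ending outcome collection.
- Seek Visit #3 data unless consent is withdrawn or the provisions of section 6 apply. Section 6 itself is left as it is.
- Record withdrawal reasons in coded categories and report them by arm.

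Reconcile:
- sections 1, 3, 4.4 and 7.1 on who is blinded;
- section 3 and the Visit #1 and group assignment texts of section 4.4 on when randomisation occurs relative to confirmed eligibility;
- the haemoglobin limits in sections 4.2 and 4.4.

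Cost: mainly protocol wording, plus some effort to obtain Visit #3 data from subjects who stop drug. A few ineligible subjects stay in the primary analysis and may dilute the effect slightly.

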5. SAFETY ASSESSMENTS

Subjects will be monitored for safety during the study period in accordance with Steglatro (ertugliflozin) package insert. In accordance with UH IRB regulations, the following documentation will be maintained in the study binder:

5.1 Adverse Events and Serious Adverse Events

The UH IRB has well-established polices (and means) for Prompt Reporting of unanticipated problems involving risk to subjects or others and these policies will be strictly followed. Any non-serious adverse event, either study or not study related, can be reported by the research team at the date of the next continuing review. Any adverse event that is considered serious and is study related must be reported to the UHCMC IRB within 5 business days; however, if the serious adverse event is non-study related, the event can be reported at the next continuing review. In addition, if a serious adverse event occurs, results in the death of a participant, and is study related, the event must be reported to the UHCMC IRB within 5 business days. However, if the event results in a death but is non-study related, the event can be reported to the UHCMC IRB at the next continuing review. The same reporting schedule will be used to communicate information on adverse events to the FDA.

	Study Related	Not Study Related		
Death	within 5 business days	at next Continuing Review		
Serious	within 5 business days	at next Continuing Review		
Non-serious	at next Continuing Review	at next Continuing Review		

5.2 Reporting Procedures

Any member of the research team will report any unexpected event or problem and any adverse event, either serious or non-serious, to the principal investigator immediately upon discovery. The principal investigator will then proceed to report the event within the specified timeframes mandated by the UHCMC IRB and the Food and Drug Administration.

5.3 Follow up for Adverse Events

Participant follow up will be one of a case by case basis as directed by the physician.

6. INTERVENTION DISCONTINUATION

Study procedures and interventions will be discontinued immediately if the any of the following occur:

- Volunteer decides that he/she would no longer like to continue with the study
- Side effects of the study drug prevent further safe use
- Study personnel identify a concern with the condition of the subject

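### Section 6 ends study procedures together with study drug, so a subject stopped under it has no post-baseline value for any declared endpoint and leaves the comparison

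*Combined protocol and SAP*

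**What the plan says.** Section 6, although headed as intervention discontinuation, covers more than the tablet: "Study procedures and interventions will be discontinued immediately if the any of the following occur". Besides the volunteer's own decision to leave, it lists two triggers: "Side effects of the study drug prevent further safe use" and "Study personnel identify a concern with the condition of the subject".

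The schedule in Section 4.3 places metabolic-cart VO2, cardiac MRI and β-hydroxybutyrate at baseline and at Visit #3. Weeks 4 and 8 are telephone calls with no endpoint measurement. Section 4.4 says that at Visit #3 "the subject will undergo a repeat of the same battery of clinical testing as during Visit #2", and times this in week 12, before the tablet supply is used up.

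Section 4.4 also accepts that "it is possible that subjects will be withdrawn from the study". For that case it asks for a case report form, not an early-termination exercise test. Section 5.3 adds only: "Participant follow up will be one of a case by case basis as directed by the physician".

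Section 7.2 specifies a t test or a Wilcoxon two-sample test. Sections 7.1 and 7.2 name no analysis set, no method for missing data and no allowance for dropout.

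**The concern.** Stopping a drug and ceasing to be measured are separate events, and Section 6 joins them. Followed literally, it withholds the only follow-up measurement from subjects whose course on treatment went badly enough for them to be stopped. The primary endpoint and both declared secondary endpoints are lost together. No intermediate value exists from which a later analysis could recover them.

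At stake is the randomised comparison. If stopping is more common in one arm, and those stopped would have done worse than those who stayed, the week-12 contrast compares subjects who remained in each arm and no longer the groups as randomised. Two features make unequal stopping plausible. Genuine side effects of ertugliflozin can occur only in the ertugliflozin arm. The personnel-concern trigger is open-ended in a trial that Section 3 calls "single blinded (to patient), randomized, parallel group, active controlled, single center experimental design". Section 7.1 says that the study team maintains blinding, and that has to be reconciled with Section 3 before one can say whether staff judgement is shielded from allocation.

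**Working it through.** **1. The plan's own sample size.** Section 7.2 gives k = 2, alpha = 0.05, beta = 0.2, f = 0.4 and 26 subjects, read here as per arm to match the 26 + 26 in Section 3. Power is taken from the noncentral F distribution with noncentrality N × f².

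- 25 per arm: 50 × 0.16 = 8.00, power 0.7915.
- 26 per arm: 52 × 0.16 = 8.32, power 0.8075.

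The figure of 26 reproduces. It is the smallest number that reaches 80% at f = 0.4, so it holds no reserve for loss. (For two groups f = 0.4 is a standardised difference of 0.8, or 1.6 ml/kg/min at the stated SD of 2.0. The text states 2.0, a standardised difference of 1.0. That mismatch is a separate matter, so both values are carried below.)

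**2. What happens to a subject stopped under Section 6.** Section 6 ends procedures. Section 4.3 has no endpoint measurement between baseline and Visit #3. Section 4.4 asks for a form. Section 5.3 leaves follow-up to the physician. None of these restores the week-12 test, so no change score exists and the subject cannot enter a two-sample test on change.

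**3. Bias from the loss.** Let m1 and m0 be the fractions lost on ertugliflozin and placebo. Let g be the amount (ml/kg/min) by which the mean change in those lost would have fallen below that of completers in the same arm. The full-arm mean is the completers' mean minus m × g, so completers overstate their arm by m × g. The bias in the difference is

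(m1 − m0) × g, with the same g in both arms.

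The documents give neither m nor g, so all values below are assumptions. Standard error = 2.0 × √[1/(26(1 − m1)) + 1/(26(1 − m0))].

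| m1 / m0 | g = 1 | g = 2 | g = 3 | SE |
|---|---|---|---|---|
| 10% / 5% | 0.05 | 0.10 | 0.15 | 0.577 |
| 15% / 5% | 0.10 | 0.20 | 0.30 | 0.586 |
| 20% / 5% | 0.15 | 0.30 | 0.45 | 0.595 |
| 5% / 5% | 0 | 0 | 0 | 0.569 |

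Against the 2.0 target: 0.05 / 2.0 = 2.5% and 0.45 / 2.0 = 22.5%. In these scenarios the bias favours ertugliflozin. It would change sign if placebo lost more subjects, or if those lost would have done better than completers.

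**4. Power after loss (counts assumed, ertugliflozin / placebo).**

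| Analysed | Standardised difference 0.8 | Standardised difference 1.0 |
|---|---|---|
| 26 / 26 | 0.807 | 0.942 |
| 25 / 26 | 0.799 | 0.938 |
| 23 / 26 | 0.782 | 0.928 |
| 20 / 24 | 0.733 | 0.897 |

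**The case against.** **Section 6 may not mean this.** It is a short safety list. It does not say that Visit #3 is cancelled or that the subject is withdrawn. Section 4.4 treats withdrawal separately and lists refusal of further testing as one ground, which suggests that testing otherwise continues. It also says that all 52 subjects will have echo at baseline and at completion. This stands in part: the intention may be better than the wording. But the wording names procedures and says immediately, the echo sentence does not cover peak VO2, and no available passage provides an off-drug Visit #3. The text between Sections 8.3 and 9.12 was not available and could bear on this.

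**The trigger is narrow.** A reader might infer that any side effect ends testing. It does not: the side effect must prevent further safe use. A subject who merely stops taking tablets is not expressly covered either.

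**Arm selectivity is not documented.** A reader might infer that loss will differ by arm. No discontinuation rate appears, overall or by arm, and blinded placebo subjects can also be stopped for events attributed to the drug. Unequal loss is a reasonable inference and no more.

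**The size is modest.** Even 0.45 is below one standard error (about 0.6), and a deficit of 3 is 1.5 times the stated SD. Power at the stated 2.0 / 2.0 stays at or above 0.897 in the cases shown. Both observations stand. But bias, unlike sampling error, is not reflected in the confidence interval.

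**The trial is mechanistic.** Testing before the tablets run out points to an on-drug question, and off-drug values dilute that effect. This is fair, and it is why an on-drug analysis belongs in the plan. It does not justify leaving the measurement uncollected, because without it neither question can be examined in those subjects.

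**Conclusion.** The point holds as a defect in a stated rule. Followed as written, Section 6 discards the only post-baseline outcome of subjects stopped for serious enough drug side effects or a staff concern, and the planned tests then use only those who reached Visit #3.

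Whether this biases the trial depends on unequal loss or unequal deficits between arms, which the documents neither show nor exclude. Under the stated assumptions (10-20% against 5% lost, deficit 1-3 ml/kg/min) the bias is 0.05-0.45 ml/kg/min. With equal losses and deficits it is zero.

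A reader might also work out the shift in the ertugliflozin mean alone, 0.10 × 1 = 0.1 to 0.20 × 3 = 0.6 ml/kg/min, and call that the bias. That sets placebo loss at nil, which nothing in the documents supports. The effect on power is secondary.

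**What to change.** Leave the drug-stopping criteria, the personnel-concern trigger and the investigator's right to withdraw a subject unchanged. Reconcile Section 6 with the Visit #3 and withdrawal text in Section 4.4, so that stopping study drug does not by itself end outcome collection. For a subject who has stopped drug, seek Visit #3 at the planned time, or whatever parts of it the subject agrees to and the study physician considers safe.

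In Section 7.2, state that subjects are analysed in the arm to which they were randomised, with an on-drug analysis as supportive, and say how any Visit #3 values still missing are handled.

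The amendment should not say that only withdrawal of consent ends data collection. That would override the safety and investigator-withdrawal provisions in Sections 6 and 4.4.

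The cost is a wording amendment with no new procedure. The downside is that some off-drug values slightly dilute the mechanistic on-drug effect, which the supportive analysis addresses.
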